#### **9.4.5. Operational Variable(s) Definition**

As is indicated in 9.4, for women who self-enroll, maternal characteristics will be provided by the pregnant woman at study enrollment. After the woman provides consent and medical release for her HCP(s) to provide data, the therapeutic or obstetric HCP will provide prenatal data (LMP, EDD, and CEDD), prenatal test data (test, date of test, and result), obstetrical history (previous pregnancy outcomes, births with congenital malformations, and family history of congenital malformations), concomitant medical conditions, concomitant medications and vaccines, and alcohol, tobacco, and illicit drug use. At pregnancy outcome, the obstetric HCP will provide pregnancy outcome data (live birth, stillbirth, SAB, elective termination, or ectopic or molar pregnancy) and infant outcome data (gestational age, birth weight, and gender). In case data on the pregnancy outcome cannot be obtained from the HCP, the pregnant woman will be asked to provide information on the pregnancy outcome. The infant's HCP will provide information at 4 and 12 months of age.

#### **9.4.6. Scientific Advisory Committee**

A Scientific Advisory Committee (SAC) will be established to oversee the scientific affairs of the study, including its ongoing monitoring. A charter for SAC activities, roles and responsibilities and meeting frequency will be established at study start. The SAC will comprise recognized experts including (but not limited to) the fields of teratology, epidemiology, maternal and fetal medicine, as well as migraine treatment. The SAC will meet regularly to review the accumulated body of data from the study, including review and classification of reported MCMs and other events of interest, and to carry out any actions required, including review and interpretation of interim data analyses and reports and publications of study data. The SAC may meet on ad hoc occasions if indicated. In addition to the above activities, the SAC might support in the design and implementation of strategies to heighten awareness of the study.

## 9.5. Study Size

The study aims to enroll a minimum of 420 prospectively enrolled evaluable pregnant women with galcanezumab exposure. Approximately 420 galcanezumab exposed pregnancies are needed to have 80% power to detect a 2.0 fold difference in the baseline risk of major malformations (2.78%) relative to women in the general population.

Assuming 10% loss to follow-up, it is anticipated that approximately 470 patients need to be enrolled. Research indicates that approximately 83% to 95% of pregnancies enrolled in pregnancy exposure registries result in a live birth (Covington et al. 2010), resulting in a lower estimate of approximately 350 and an upper estimate of 400 live births.

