**Exclusion:**

- Patients with known pregnancy outcomes at the time of enrollment
- Variables:

*Exposure:* treatment with galcanezumab at any time during pregnancy or up to 4 months prior to conception.

*Outcomes:*

- Congenital malformations: major and minor malformations
- Pregnancy outcomes: recognized spontaneous abortions, ectopic pregnancy, molar pregnancy, stillbirths, elective terminations

- Maternal pregnancy complications: preeclampsia and hypertension in pregnancy
- Infant outcomes at birth: preterm birth, small for gestational age infants
- Infant events of interest (up to one year of age): postnatal growth and development
- Data sources: The pregnant woman and appropriate members of her and her infant's health care team will serve as data reporters to the study. The study is strictly observational; patient care and treatment regimens will be determined by the treating HCP.
- Study size: The study aims to enroll a minimum of 420 prospectively enrolled evaluable (i.e., those for whom outcome of pregnancy including presence/absence of any congenital malformations was obtained) pregnant women with galcanezumab exposure, as well as 420 untreated migraine controls (i.e., not treated with galcanezumab or other CGRP antagonists but *may* have been treated with other prescribed or over-the-counter migraine therapies) and 420 non-migraine, general population controls (i.e., do not suffer from migraines).

Data analysis: Demographic and baseline characteristics will be summarized with descriptive statistics for the galcanezumab exposed group as well as for the two comparison groups.

Proportions and 2-sided, 95% confidence intervals will be calculated using the exact binomial distribution for prevalence of congenital malformations among evaluable patients, preterm birth and SGA among patients with live births, preeclampsia and hypertension in pregnancy and infant growth and development through one year. Rates will be presented overall and stratified by timing of exposure.

- Where statistically feasible, the relative occurrence of maternal, pregnancy and infant outcomes among women exposed to galcanezumab as compared to 1) women with migraine not exposed to CGRP antagonists and 2) women without migraine will be estimated.
- Milestones: The study will be open for enrollment beginning 01 March 2020. The estimated end of data collection is 30 November 2032, and the Final Study Report will be submitted 30 November 2033.

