#### 9.2.2. Study Participants

The study population will include pregnant women within the US who were treated with galcanezumab as part of routine care at any time during pregnancy or up to 4 months prior to conception, as well as pregnant women with migraine not exposed to CGRP antagonists and pregnant women without migraine. Eligible pregnant women may self-enroll or voluntarily be enrolled by their HCP. Enrollment should occur as early in pregnancy as possible, preferably before any prenatal testing has occurred.

Enrollment and data collection will be coordinated through the Registry Coordination Center (RCC). The minimum eligibility criteria required for enrollment are as follows:

Inclusion:

- Pregnant at the time of enrollment

- Sufficient information to confirm eligibility for either the galcanezumab, unexposed to CGRP antagonist, or general population cohort
  - Galcanezumab cohort: at least one injection of galcanezumab occurred during the pre-pregnancy or pregnancy period (as defined in Section 9.3.1) without any other CGRP antagonist exposure during this time and at which date
  - Unexposed to CGRP antagonist cohort: no exposure to a CGRP antagonist during the pre-pregnancy period (as defined in Section 9.3.1)
  - General population (without migraine) cohort: no diagnosis of migraine
- Sufficient information to determine whether the outcome of pregnancy is known at the time of registry reporting to determine whether the pregnancy exposure reported to the registry is prospective (i.e., before the outcome or perceived outcome of pregnancy is known) and eligible for enrollment
- Reporter (e.g., participant, maternal HCP) contact information to allow for follow-up
- Permission to contact the patient's and her infant's HCPs
- Patient informed consent to participate

Exclusion:

- Retrospective (i.e., a pregnancy exposure to the Registry drug reported after the pregnancy has ended or for an ongoing pregnancy in which an abnormal condition was identified on a prenatal test) cases are ineligible for enrollment
- Women under 18 years of age

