### **9.7.2. Statistical Methods**

Overall and stratum-specific (e.g., timing of exposure to galcanezumab (prior to conception vs. during pregnancy, as well as trimester of exposure), maternal age group) point estimates and 2-sided 95% confidence intervals will be calculated using the exact binomial distribution for prevalence of congenital malformations among evaluable patients, preterm birth and SGA among evaluable patients with live births, preeclampsia and hypertension in pregnancy and infant growth and development through one year for each of the galcanezumab exposed, CGRP antagonist-unexposed migraine and general population, non-migraine groups.

If applicable, frequencies of the events of interest will be presented by pregnancy outcome.

Most structural defects have their origins in the first trimester of pregnancy, the period of organogenesis. In addition to overall prevalence of observed MCM, the analysis of MCMs will be stratified by trimester of earliest exposure to galcanezumab. The prevalence of combined MCMs reported to the study will be calculated as a proportion with the number of observed MCMs as the numerator and the number of live births as the denominator, among women with first trimester exposure. CDC MACDP uses these figures to calculate the prevalence, and in order to compare the observed study prevalence with the background prevalence, it is decided to use the same method. Pregnancy losses occurring at or after 20 weeks' gestation with reported MCMs will be included in the numerator of the estimate of prevalence for MCMs as a conservative approach. This method also allows comparison of outcomes with the CDC MACDP. The reason MACDP uses this method is because a slight overestimate is preferred to a potential underestimate. This is due to not taking into account stillbirths in the denominator (but counting the MCM's recognized in stillbirths in the numerator). However, given the very low prevalence of stillbirths as pregnancy outcomes in the general population, this is only a very small possible overestimate. The prevalence of observed MCMs in exposed cases will be compared with the most recent reported prevalence of the CDC MACDP. Additionally, if a sufficient sample size is attained for each trimester exposure group, it may be possible to compare the prevalence of MCMs among exposures to galcanezumab in the first trimester versus

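### Section 9.5's 80% power belongs to 420 exposed pregnancies of any outcome and exposure timing, not to the first-trimester live-birth malformation prevalence that section 9.7.2 builds for the background comparison

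*Protocol*

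**What the plan says.** **Target.** Protocol section 9.5 states: "Approximately 420 galcanezumab exposed pregnancies are needed to have 80% power to detect a 2.0 fold difference in the baseline risk of major malformations". It puts that baseline at 2.78%, the general-population figure. The enrolment aim in the same section is a "minimum of 420 prospectively enrolled evaluable pregnant women with galcanezumab exposure". The Abstract (section 4, study size) explains evaluable as "those for whom outcome of pregnancy including presence/absence of any congenital malformations was obtained". Neither place restricts the pregnancy outcome or the timing of exposure.

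**Exposure window.** Section 9.2.2 admits women treated "at any time during pregnancy or up to 4 months prior to conception". A woman first exposed in the second or third trimester therefore counts towards the 420.

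**Malformation estimates.** Section 9.7.2 plans two. One is an overall prevalence among evaluable patients. The other is a combined MCM prevalence with "the number of live births as the denominator, among women with first trimester exposure"; losses at or after 20 weeks with an MCM are added to its numerator. The section says this second method was chosen so that the result can be set against the MACDP background prevalence. Section 9.9 adds that losses without a diagnosed MCM are left out of the MCM calculation.

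**Expected live births.** Section 9.5 assumes 10% loss to follow-up, about 470 enrolled and an 83% to 95% live-birth share, "resulting in a lower estimate of approximately 350 and an upper estimate of 400 live births". It does not repeat the power statement for that number.

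**The concern.** The protocol fixes both the target and the estimate, so this is not a detail left to the analysis plan. The power statement is about a fixed population rate. The estimate built for comparison with such a rate uses a smaller set than the 420: live births only in the denominator, and only women with first-trimester exposure.

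Enrolment starts in 2020 and data collection ends in 2032, with annual reports. The registry could truthfully report that it had reached its minimum while the ratio compared with the background rested on fewer pregnancies. A reader of an unremarkable result could then credit that comparison with 80% power to detect a doubling, which section 9.5 never showed for it.

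**Working it through.** **Inputs.** From section 9.5: baseline p0 = 0.0278; doubled risk p1 = 0.0556; n = 420; power 80%; loss to follow-up 10%; live-birth share 83% to 95%. Alpha, sidedness and test are not stated there. The first-trimester share is not given anywhere, so it is an assumption below.

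**1. Reproducing 420.**
- One-sample normal formula, one-sided 5%, variance at p1: n = (1.645 + 0.842)² × 0.0556 × 0.9444 / 0.0278² = 420.06.
- Exact binomial test against a fixed 2.78%, upper tail 0.025: at n = 420 it rejects with 20 or more cases, true size 0.0152, power 79.1%. Power stays at or above 80% from n = 423.
- Two-sample 1:1 comparison, as the planned controls would require: 811 per group two-sided, 639 one-sided. Neither is near 420.

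So the figure reproduces against a fixed background rate and not against the 1:1 internal controls.

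**2. Reproducing the accrual figures.** 420 / 0.9 = 467, about 470. 420 × 0.83 = 349 and 420 × 0.95 = 399, about 350 and 400. The 420 therefore includes pregnancies that do not end in a live birth.

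**3. Power on live births.** Normal formula from step 1: power = Φ(0.0278 × √n / √(0.0556 × 0.9444) − 1.645). Exact power is saw-toothed in n, so it is evaluated at every n in the range rather than only at the ends. The 80% first-trimester share is assumed.

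| Set | n | Normal, one-sided 5% | Exact, upper tail 0.025 |
|---|---|---|---|
| Section 9.5 target | 420 | 80% | 79% |
| Live births, all first-trimester exposed | 350 to 400 | 73% to 78% | 71% (n = 360) to 81% (n = 386), average 76% |
| Live births, 80% first-trimester exposed | 280 to 320 | 65% to 70% | 60% (n = 280) to 72% (n = 304), average 66% |

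**4. Detectable ratio at 80% power.** Setting power to 0.80 in the same normal formula and solving for p1/p0 gives 2.00 at n = 420, 2.03 at 400, 2.13 at 350, 2.20 at 320 and 2.31 at 280.

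**5. Which women are in the first-trimester set.** Section 9.4.3 treats an injection from four months before LMP as fetal exposure and classifies by earliest trimester, with no pre-conception category. Section 9.7.2 offers exposure before conception versus during pregnancy as an example of a separate timing stratum. If women exposed only before conception count as first trimester, the share could be near 100% and the second row of the table applies. If they do not, a lower row applies, and how low is unknown.

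**The case against.** The strongest reply is that section 9.5 does match one planned estimate. Section 9.7.2 plans an overall malformation prevalence among evaluable patients and presents the trimester analysis as an addition to it. Its sentence on the MACDP comparison refers to exposed cases generally. The primary objective is descriptive, exact 95% intervals will show the precision achieved, and section 9.5 openly discloses 350 to 400 live births.

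Most of this stands, and it limits the point. A reader might infer that the women planned for are simply not the women analysed. The protocol does not support that: there are two estimates and the 420 fits one. But the first-trimester live-birth ratio is the one given an explicit numerator and denominator for the sake of the background comparison, and that is the kind of comparison from which 420 follows. Disclosing the live births does not attach a power to them.

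Other stronger readings also fail:
- That women exposed only before conception fall outside the first-trimester set. Section 9.4.3 leaves this open.
- That power collapses to half or less. This needs a low first-trimester share for which the protocol gives no basis.
- That malformation status is often unknown after a loss, so 470 enrolled cannot yield 420 evaluable. Section 9.9 says only that the physician may not know.
- That the estimate uses live births alone. This is true of the denominator, but later losses with an MCM enter the numerator.

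The result also depends on the formula. A two-sided one-sample normal test using both null and alternative variances gives 80.6% at 350 and 84.6% at 400. That formula needs only 344, however, so it is not how 420 arose.

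**Conclusion.** The point holds in limited form. The 80% in section 9.5 is not the power of the first-trimester live-birth MCM prevalence in section 9.7.2. On the protocol's own live-birth range the shortfall is modest: about 73% to 78% by the formula that returns 420, or 71% to 81% (average 76%) by the exact test. It grows with any first-trimester share below 100%, to about 60% to 72% (exact) at an assumed 80%.

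These sizes rest on a fixed 2.78% reference, a true doubling and an alpha and test inferred from reproducing 420. The 80% share is illustrative. The mismatch itself needs none of these assumptions; it follows from the wording of sections 9.5 and 9.7.2. It makes the power statement unclear and too favourable for one estimate. It does not invalidate the registry or show that it must enrol more women.

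**What to change.** 1. In section 9.5, say which MCM estimate the 420 and the 80% refer to, and state alpha, sidedness and test.
2. Add power and detectable ratio for first-trimester-exposed live births expected from 470 enrolled, over a stated range of first-trimester shares, using section 9.7.2's own denominator.
3. Reconcile sections 9.4.3 and 9.7.2 on whether exposure only before conception counts as first trimester for this estimate.
4. In the annual reports, tabulate accrual by exposure timing (before conception only, first trimester, later first exposure) and by live birth, beside the total towards 420.

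The cost is one rewritten paragraph, one clarified definition and one table per report. No extra enrolment is needed. The downside is a less favourable stated power for the background comparison.

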## 9.6. Data Management

Patient data are recorded on data forms. RCC study personnel are responsible for the integrity of the data (that is, accuracy, completeness, legibility, and timeliness) reported to Lilly.

All patients who provide consent to release information and who fulfil the study entry criteria will be included in the analyses. For those patients who are lost to follow-up, or who drop out of the study, the analyses will include all data up to the point of their last data collection.

### 9.6.1. Data Processing

Data for this prospective observational safety study will be managed with an electronic data capture (EDC) platform, Cisiv Baseline Plus, which is 21 CFR Part 11 compliant. Only the variables described in the protocol under section 9.3 will be solicited and entered in the EDC. Participants and/or their HCPs will provide data over the phone or by completing a paper case report form (CRF), which can be submitted to the RCC via mail, email or fax. The data will be reviewed by a registry central monitoring associate (CMA) associate for correctness and completeness and entered into the database.

### 9.6.2. Software and Hardware

Data analyses will be performed using the statistical software program, SAS (version 9.2 or higher; SAS Institute, Cary, NC).

## 9.7. Data Analysis

Descriptive analyses for the primary study objective will be performed for all data annually. For the secondary study objective, analyses of relative occurrence of the study outcomes for galcanezumab exposure compared to the two comparator groups will be performed if statistically feasible.

The summary statistics for continuous and categorical variables to be used will be specified in the statistical analysis plan (SAP) but may include means, standard deviations, medians, minimums, maximums, percentiles, n's, percentages and 2x2 tables to reflect the number of events of interest per pregnancy outcome.

The study will identify the number of cases for congenital malformations, pregnancy outcomes, maternal pregnancy complications, and infant outcomes and events of interest as described in Section 8. Proportions of these outcomes will be calculated with 95% confidence intervals from the total number of pregnant women, or live births as appropriate. Stratification may be done by earliest trimester of exposure, pregnancy outcome (for events of interest only), maternal age and other relevant variables, where applicable.

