#### 9.2.1. Study Period

The study will be open for enrollment beginning March 2020. The data collection process for each participant will begin at enrollment (during pregnancy), and follow-up will occur at the end of the second trimester (approximately 24 weeks' gestation) and/or at pregnancy outcome (delivery or early termination). The second trimester pregnancy follow-up may not be applicable for women who enroll late in pregnancy. If a live birth is reported, the Registry conducts follow-up at 4 and 12 months of age.

An annual interim study report, reviewed by the SAC, will be submitted to the Center for Drug Evaluation and Research (CDER) beginning November 2020. The Interim Report summarizes the status and the cumulative data, current to the most recent annual data cutoff period. The estimated end of data collection is 30 November 2032. The last annual report will be submitted November 2031 and the final report will be submitted November 2033.

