##### **9.2.4.1. Internal Comparison Groups**

The registry will attempt to enroll 420 women with migraine not exposed to CGRP antagonists (i.e., not treated with CGRP antagonists but *may* have been treated with other prescribed or over-the-counter migraine therapies) and 420 general population controls (i.e., do not suffer from migraines). While women with migraines untreated with any therapy may be included in the comparison group, the comparison group should not be made up entirely of untreated women. Migraines are associated with some baseline pregnancy risks and comorbidities and limiting to untreated controls may introduce bias among a group of women with less severe disease,

exposure to other migraine treatments or other fundamental population differences with potentially differential pregnancy outcomes.

For the CGRP antagonist-untreated migraine controls, the reporting HCP for the galcanezumab-exposed pregnant women will be asked to identify and enroll a CGRP antagonist-unexposed migraine control patient (but who may have been treated with other prescribed or over-the-counter migraine therapies). This will help to ensure that there is general balance in the overall registry enrollment. Should the reporting physician not be able to identify an eligible CGRP antagonists-unexposed control patient, the internal comparison group could be supplemented with self-referred pregnant women who suffer from migraines. Additionally, the subset of dedicated reporting physicians (see above) can serve as a source of CGRP antagonist-unexposed pregnant migraine patients.

Reporting maternal HCPs, including the group of dedicated reporting physicians (see above) can serve as referral sources of pregnant women with migraine, as well as the general population controls without migraine. For the general population controls without migraine, an additional supplemental approach, if needed, will be to invite enrolling women in either the galcanezumab exposed or GCRP antagonist-unexposed groups to “refer a friend” without migraines to participate. The internally enrolled general population controls without migraine approach will provide a directly comparable background comparison group overcoming the traditional limitations of external comparators.

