#### **9.3.2. Congenital Malformations, Pregnancy Outcomes, Maternal Pregnancy Complications, Infant Outcomes and Infant Events of Interest**

##### **9.3.2.1. Pregnancy outcome**

Each **pregnancy outcome** will be reported as one of the following:

- Live birth: an infant born alive
- Stillbirth: a fetal death occurring at 20 weeks' gestation or greater, or if gestational age is unknown, a fetus weighing 500 g or more
- Recognized spontaneous abortion (SAB): fetal death or expulsion of products of conception prior to 20 weeks' gestation. Terminology may include missed abortion, incomplete abortion, and inevitable abortion.
- Elective termination: voluntary interruption of pregnancy, including pregnancy termination that occurs electively, to preserve maternal health, or due to abnormalities
- Ectopic pregnancy: implantation of a conception outside of the uterus
- Molar pregnancy: a conception that results in a gestational trophoblastic tumor

Maternal death will be assessed on a case-by-case basis to determine if it is an evaluable or non-evaluable patient.

Pregnancy outcomes may occur in presence or absence of a congenital malformation (see Section 9.3.2.2).

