Migraines are associated with some baseline pregnancy risks and comorbidities. It will be important to compare the galcanezumab-exposed, CGRP antagonist-unexposed migraine controls and general population controls for population differences which may potentially result in differential pregnancy outcomes and the introduction of bias.

An important potential limitation of this pregnancy registry is the possibility of lower than expected enrollment. This can result either because galcanezumab is not being prescribed to pregnant women, or because exposed women are not being reported/enrolled into the registry. If enrollment projections are not being met, it will be important to understand why and to identify additional strategies for increasing registry enrollment.

Requiring women to be pregnant at the time of enrollment means that spontaneous abortions occurring early in pregnancy may not be included in the registry. Only recognized spontaneous abortions occurring after enrollment will be captured. It is important to enroll women as early in pregnancy as possible and before the results of prenatal tests are known to maximize the number of prospective enrollments into the registry.

Potential biases related to the composition of the two comparison groups will need to be considered. The non-CGRP antagonist treated migraine controls *may* have been treated with other prescribed or over-the-counter migraine therapies (e.g. anti-epileptic medications including topiramate, tricyclic anti-depressants, beta-blockers, or triptans) which can themselves be associated with pregnancy outcomes, maternal pregnancy complications, and/or maternal comorbidities associated with infant outcomes. If statistically feasible, the impact of type of migraine therapy in this control group could be assessed in sensitivity analyses. Additionally, there may be differences in migraine severity between the galcanezumab-exposed and the CGRP antagonist non-exposed migraine controls. The impact of migraine itself will be taken into account by describing and where possible evaluating the relative occurrence of the study outcomes in the galcanezumab exposed and the non-CGRP antagonist exposed migraine groups vs. the non-migraine control group, as well as potentially with published external comparison data. If the number of women in the registry is small, baseline differences between the exposure cohorts may not be overcome, limiting the ability of the registry to provide meaningful conclusions.

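### Spontaneous abortion is estimated as a crude proportion of all pregnant women although women may enrol at any gestational age, so enrolment timing alone can create or hide a difference between cohorts

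*Protocol*

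**What the plan says.** Section 9.7 covers all study outcomes, pregnancy outcomes included: "Proportions of these outcomes will be calculated with 95% confidence intervals from the total number of pregnant women, or live births as appropriate". The same section adds that "analyses of relative occurrence of the study outcomes for galcanezumab exposure compared to the two comparator groups will be performed if statistically feasible".

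Section 9.3.2.1 defines spontaneous abortion as "fetal death or expulsion of products of conception prior to 20 weeks' gestation". Section 9.2.2 encourages early enrolment but sets no upper gestational-age limit, and section 9.2.1 expects late entrants: "The second trimester pregnancy follow-up may not be applicable for women who enroll late in pregnancy". Section 9.9 concedes that "Only recognized spontaneous abortions occurring after enrollment will be captured".

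On recruitment, section 9.2.4.1 first asks the provider who reported an exposed woman to find a migraine control. Failing that, "the internal comparison group could be supplemented with self-referred pregnant women who suffer from migraines". Women without migraine may come from providers or through a refer-a-friend scheme.

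Two other provisions bear on the point. The subgroup paragraph of section 9.7.2.1 lists gestational age at enrolment as a possible stratifier, without committing to it. Section 9.6 says "All patients who provide consent to release information and who fulfil the study entry criteria will be included in the analyses", and that women lost to follow-up contribute data up to their last collection.

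**The concern.** A woman is at risk of a recorded abortion only from enrolment to week 20. One who enrols at week 14 has already come through the earlier weeks, and one who enrols at week 20 or later cannot have the outcome at all. Both count fully in the denominator. The crude proportion therefore mixes the risk of loss with the distribution of enrolment times.

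Stillbirth and elective termination share the problem to a lesser degree. Stillbirth risk starts only at week 20, so a woman enrolled before then is observed through the whole window. Terminations before enrolment are unseen, as early losses are.

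Pregnancy outcomes are part of the primary objective and of the secondary, comparative objective. If one cohort enrols earlier than another, its crude abortion proportion is higher with no difference in risk. If exposed women enrol later than controls, a real excess can be masked. In a safety registry, masking is the more serious error.

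**Working it through.** **What the protocol supplies.** The abortion window closes at week 20 (9.3.2.1), losses are seen only after enrolment (9.9), entry is open (9.2.1, 9.2.2), and the target is 420 women per cohort (9.2.4.1, 9.5). It gives no abortion risk, hazard shape or distribution of entry weeks, so there is no figure of its own to reproduce. The values below are assumptions, shown as ranges.

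**Late entrants, no hazard assumption needed.** If a share s of a cohort enrols at or after week 20, the crude proportion is (1 − s) × p, where p is the proportion among earlier entrants. An assumed s of 20% lowers it by 20% in relative terms.

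**Main illustration.** The weekly hazard in week w is h(w) = h(5) × r^(w−5) for w = 5 to 19. It is scaled so that 1 − Π(1 − h(w)) = 12%, giving h(5) = 0.0160 for r = 0.9 and 0.0263 for r = 0.8. If every woman in a cohort enters at week e, the crude proportion is 1 − Π(1 − h(w)) over w = e to 19. True risk is the same in all cohorts.

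| Entry week | r = 0.9 | r = 0.8 |
|---|---|---|
| 8 | 8.07% | 6.10% |
| 10 | 5.99% | 3.78% |
| 14 | 2.87% | 1.30% |
| 20 | 0% | 0% |

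False ratios:
- Week 8 versus 10: 8.07/5.99 = 1.346 and 6.10/3.78 = 1.61, so 1.3 to 1.6.
- Week 8 versus 14: 8.07/2.87 = 2.8 and 6.10/1.30 = 4.7. This is extreme, because it needs all of one cohort at week 8 and all of the other at week 14.

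**Wider assumptions.** Total risk was set at 10%, 15% or 20%, with the hazard proportional to exp(−d(w − 5)) and d from 0 (flat) to 0.3.
- Week 10 versus 12, no true difference: ratio 1.23 to 1.90.
- Week 8 versus 12, no true difference: ratio 1.46 to 3.51. With 420 per group, the chance of a nominally significant result (two-sided 0.05) is 33% to 97%. For example, 15% risk with d = 0.1 gives 10.25% versus 5.55%, ratio 1.85, chance 72%.
- Masking: with a true hazard ratio of 1.5, exposed women entering at week 12 and controls at week 8, the crude ratio is 1.00 down to 0.43.

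**After the change.** With risk sets conditional on gestational age at entry, the same scenarios return the true hazard ratio by construction: 1.0 where there is no effect, 1.5 where that effect was built in.

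**The case against.** The strongest reply is that little is fixed. Section 9.7 mainly serves a descriptive objective, the comparison is conditional on feasibility and has no stated estimator, and confounding and stratification details are left to the SAP, which is not at hand. A descriptive proportion does not rule out a time-to-event model. The protocol also acknowledges missed early losses, urges early enrolment, has the provider of an exposed woman enrol a migraine control to help balance, and names gestational age at enrolment as a possible stratifier. The entry gaps in the illustration are hypothetical.

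Much of this is fair. It is wrong to say that the plan does nothing about entry time, and the sizes above show sensitivity and do not forecast. But the proportion and its denominator for pregnancy outcomes are stated in the protocol, and they are hard to interpret even descriptively without entry time. The limitations text changes no estimator, the stratifier is optional, coarse strata correct only partly, and nothing matches cohorts on gestational age at entry.

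A reader might infer more than the protocol supports:
- **Event-free time before a late first injection.** Sections 4 and 9.2.2 require at least one injection, with its date, for eligibility for the galcanezumab cohort, so the first injection precedes entry.
- **A misleading exact interval.** The exact-binomial list in section 9.7.2 does not include spontaneous abortion; section 9.7 says only that intervals are 95%.
- **The same flaw in malformations, preterm birth and growth restriction at birth.** Section 9.7.2 uses evaluable or live-birth denominators for these.
- **A further 10% relative fall in every proportion from loss to follow-up.** Section 9.5 assumes that rate ("Assuming 10% loss to follow-up, it is anticipated that approximately 470 patients need to be enrolled"), but section 9.6 does not say that lost women count as non-events, and equal loss in both groups would cancel in a ratio.

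**Conclusion.** The point holds for spontaneous abortion and, more weakly, for stillbirth and elective termination. Followed as written, section 9.7 gives an abortion proportion that depends on when women enrol, and any comparison built on it inherits that dependence. The mechanism follows from the protocol alone. Its size does not: it rests on the assumed risk, hazard shape and one entry week per cohort, and will be small if the cohorts turn out to enrol at similar gestational ages. The protocol gives no assurance that they will.

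Separately, the treatment of women lost to follow-up in the abortion denominator is unclear. Section 9.6 includes all eligible consenting women, while section 9.7.2 uses evaluable women for some other outcomes. This needs clarifying; it is not a demonstrated bias.

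**What to change.** In section 9.7:
- Estimate spontaneous abortion (to week 20) and stillbirth on the gestational-age scale, with delayed entry at enrolment, censoring at last contact, and elective termination as a competing event.
- Exclude women enrolled at or after week 20 from the abortion risk set.
- Report cumulative incidence by cohort and, where the comparison is feasible, a hazard ratio.
- Keep the crude proportion as a secondary display with a known-outcome denominator, and state whether women lost to follow-up are in it.

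The cost is slightly wider intervals and a little more analysis work with standard methods. No new data are needed: sections 9.4.1.1 and 9.4.1.2 already collect the menstrual and delivery dates and the outcome date, and the enrolment date comes with registration. The method still assumes that, at a given gestational age, women who have enrolled carry the same risk as those who enrol later; it does not remove other selection into a voluntary registry.
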